Psych Assessment (MINI)	X										
Cognitive Function (WRAT)	х										
Metric Wire install and EMA training		Х									
STUDY CIGARETTES											
Randomization			Х								
Study Cigarettes Supplied			х	х	Х	х					
Product Accountability				Х	Х	х	Х				
Timeline Follow-back			Х	Х	Х	х	Х				
Urine Sample (TNEs)*				Х	Х	X	Х				
SAFETY ASSESSMENTS											
Medications	х	x	Х	Х	Х	х	Х	X			
Vital Signs	X	X	Х	Х	X	х	Х	X			
Pregnancy Test	х		Х								
Respiratory Health/ Side Effects Forms	X	×	X	×	×	×	×	X			
Adverse Events		x	х	х	X	х	х	Х			
PRIMARY AND SECONDA	RY OUTCOME	MEASURES	5	Į.			l .	Į			
Cigarette Dependence	х		х	х	Х	х	х				
Craving/Withdrawal	Х	X	х	х	Х	х	х	Х			
Pain Intensity/ Interference	x	X	Х	x	×	Х	x	х			
Quit Self-Efficacy	х		х		X		х				
Motivation to Quit	х		х		X		х				
Pain-Related Cognitions	×	×	x		Х		×	Х			

**UB:** Usual brand cigarettes; **NNC:** Normal nicotine content research cigarettes; **VLNC:** Very low nicotine content research cigarettes; **EMA:** Ecological momentary assessment; **CO:** Carbon monoxide; **M.I.N.I.:** Mi ni International Neuropsychiatric Interview; **WRAT:** Wide Range Achievement Test-4 (Word Reading Subtest); **TNEs:** Total Nicotine Equivalents

\*Note that urine samples will be collected at all visits to increase perception that study cigarette adherence may be biochemically verified at any time, but only weekly visits 4 and 5 of the VLNC group will be analyzed for TNEs.

Study Procedures. Details of specific procedures involved in the study are described below.

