Questionnaires: A standard battery of questionnaires and interview measures will be administered via Redcap to evaluate psychological, behavioral, smoking, pain and health information. These will include: demographics, a Tobacco Use History interview, a Brief Medical History questionnaire and Follow-up Form, a Medication Changes Ouestionnaire, a Health Changes Ouestionnaire, a Drug Use History guestionnaire, a Motivation to Quit Smoking questionnaire, the Alcohol Use Disorders Identification Test (AUDIT), the Fagerstrom Test of Cigarette Dependence (FTCD), the Wisconsin Inventory of Smoking Dependence Motives (WISDM), the Minnesota Tobacco Withdrawal Scale (MTWS), the Questionnaire of Smoking Urges-Brief (QSU-B), the Brief Pain Inventory-Short Form (BPI-SF), the Graded Chronic Pain Scale (GCPS), the Pain and Smoking Inventory (PSI), the Smoking Self-Efficacy Questionnaire (SEQ-12), the Center for Epidemiological Studies-Depression scale (CES-D), and a follow-up Quitting Behaviors questionnaire. Additional questionnaires may also be used, including: the Pain Catastrophizing Scale (PCS), a Smoking Cessation Therapy Use questionnaire, the Life Events Checklist (LEC), a measure of Adverse Childhood Events (ACES), Composite Morningness Scale (CMS), PROMIS Sleep Questionnaire, the Distress Tolerance Scale (DTS), and Profile of Mood States (POMS), State-Trait Anxiety Inventory (STAI), Snaith-Hamilton Pleasure Scale (SHAPS), and the Positive and Negative Affect Schedule (PANAS), the Chronic Pain Self-Efficacy Scale (CPSS), the Cigarette Evaluation Scale (CES), PATH Dependence Scale, Cigarette Expectancies (Study Cigarette & Usual Brand) Scale, Study Cigarette Purchase Task; Perceived Health Risk (Study Cigarettes & Usual Brand), Coping Strategies Questionnaire-short form, CSQ-7 item, Chronic Pain Coping Inventory (CPCI), Pain Anxiety Symptom Scale (PASS-20), and the CHOIR body map.

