# **Data Analysis & Statistical Considerations**

Describe endpoints and power calculations. Provide a detailed description of how study data will be
analyzed, including statistical methods used, and how ineligible subjects will be handled and which
subjects will be included for analysis. Include planned sample size justification. Provide estimated time
to target accrual and accrual rate. Describe interim analysis including plans to stop accrual during
monitoring. Phase I studies, include dose escalation schema and criteria for dose escalation with
definition of MTD and DLT.

Hypothesis testing will be conducted using generalized mixed models, which are well-equipped to handle missing data, even when data is missing not completely at random. Multiple imputation will also be used to further address potential bias resulting from missing data.

Specific Aim 1 will examine the effects of NNCs versus VLNCs on: a) changes in cigarettes smoked per day, nicotine dependence, withdrawal symptoms and pain across the 5 weekly visits (V1 through V5), and b) pre-post intervention changes in withdrawal and pain following 24hr abstinence. For both sets of models, Group will be entered as a between-subjects factor with 2 levels (NNC or VLNC), and Session will be included as a within-subjects factor with 5 (week) or 2 (pre- vs post-intervention) levels. Baseline pain and FTCD scores, assessed at screening, will be included along with sex as covariates. We predict that the VLNC group will exhibit decreasing nicotine dependence and smoking frequency across the 4 weeks of study cigarette use, with no change for the NNC group (i.e., Group x Week interactions). Based on our prior work, we predict only a minimal increase in withdrawal during the first week of VLNC use, with no group differences in withdrawal or pain during remaining weekly visits. During 24-hr abstinence, we predict a Group x Session interaction, such that the VLNC group will exhibit pre- to post-intervention decre ases in withdrawal and pain, with no change for the NNC group. Secondary analyses will evaluate effects of abstinence, controlling for weekly changes during ad lib smoking, by including withdrawal and pain assessed at V1 (pre-intervention) and V5 (post-intervention) as time-varying covariates.

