Specific Aim 2 will be to examine the effects of NNCs versus VLNCs on the bidirectional, within-person associations between momentary reports (assessed with EMA) of pain, negative affect, and smoking urge and behavior. Longitudinal associations between smoking/smoking urge and a) pain intensity, b) pain interference, and c) negative affect will be evaluated in separate models. The first set of models will examine each pain measure as a predictor of smoking urge/intent to smoke at each time point. The second set of models will examine recent smoking (i.e., having smoked within the past 15 minutes) as a predictor of each pain measure. Models will include repeated assessments (Level 1) nested within participants (Level 2), nested within weeks (Level 3), with random intercepts. Cigarette condition (NNC or VLNC) and its interaction with week will then be entered to examine the moderating effects of study cigarette use on these within-person associations.

Exploratory Aim 3 will examine the effects of NNCs versus VLNCs on pre- to-post-intervention changes in smoking for pain-related cognitions, assessed at V1 and V5, including smoking to cope with pain, interest in quitting smoking, quit self-efficacy, pain catastrophizing, and pain self-efficacy. For each model, Group will be entered as a between-subjects factor, and Session will be entered as a within-subjects factor.

Sensitivity Analyses will examine the potential impact of a) VLNC compliance (described above) and b) non-opioid analgesic use on the results of primary analyses. Analgesic use will be coded as yes/no at screening and at each weekly visit for the following medication classes: NSAIDS, anticonvulsants, antidepressants, other CNS depressants, muscle relaxants, migraine medications, and corticosteroids. Sensitivity analyses will then examine the impact of weekly use of each medication class as time-varying covariates in primary models.

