Sample size determination. Sample size was estimated using G\*Power 3.1, assuming 85% power at alpha=0.05 for detecting group by session interactions in Aim 1 (see Statistical Design and Power for additional details). For effect sizes corresponding to Cohen's d = 0.4 to 0.6, assuming a conservative estimate of the correlation between repeated measurements of 0.4, our proposed sample size of 48 will provide 90% to 99% power for detecting group by weekly session interactions (5 measurement occasions per group), and 70% to 96% power for detecting group by abstinence session interactions (2 measurement occasions per group). Importantly, power for detecting abstinence session interactions is improved (ranging from 77% to 98%) if repeated measures correlation is higher, as suggested by our preliminary data. These calculations also do not take into account the inclusion of baseline covariates that are likely to improve power.  Moreover, a loss of 33% of the sample due to VLNC non-compliance during sensitivity analyses will still yield statistical power of 96% and 78% for analyses with 5 measurement occasions or 2 measurement occasions, respectively, under a moderate scenario in which Cohen's d = 0.5and the correlation between repeated measures = 0.5. Given the increase in statistical power associated with EMA due to a) decreasing error variance,  and b) increasing the number of repeated assessments,  it is expected that sample sizes estimates determined for Aims 1 and 3 will provide ample power for detecting group differences in reciprocal smoking-pain associations in Aim 2.

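### Exploratory Aim 3 compares V1-to-V5 change with no baseline covariate named; adjusting V5 for the V1 value would be more precise at no cost in data

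*Combined protocol and SAP*

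**What the plan says.** In Data Analysis & Statistical Considerations, Exploratory Aim 3 concerns pre-to-post change in five outcomes, "assessed at V1 and V5, including smoking to cope with pain, interest in quitting smoking, quit self-efficacy", followed by pain catastrophizing and pain self-efficacy. The model is described in one sentence: "For each model, Group will be entered as a between-subjects factor, and Session will be entered as a within-subjects factor". No covariate is named.

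Aim 1, in the same section, does name covariates: "Baseline pain and FTCD scores, assessed at screening, will be included along with sex as covariates". That sentence belongs to the Aim 1 models, and it does not mention baseline values of the Aim 3 outcomes.

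Table 1 in Design & Procedures collects these outcomes more often than Aim 3 uses them. The rows "Quit Self-Efficacy" and "Motivation to Quit" are marked at screening, V1, V3 and V5. The row "Pain-Related Cognitions" is marked at those visits and also at the two abstinence sessions, A1 and A2. The column positions survive text extraction: the randomisation mark falls under V1, and the urine nicotine-equivalents marks fall under V2 to V5.

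Two of the five outcomes rest on optional instruments. The Questionnaires paragraph puts the catastrophizing scale, and later in the same list the chronic pain self-efficacy scale, under this opening: "Additional questionnaires may also be used, including: the Pain Catastrophizing Scale (PCS").

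**The concern.** With two groups and two sessions, and group means left free at both, the Group x Session test is a t-test on V5 minus V1. Subtracting V1 fixes the weight on the baseline at one. Adjustment lets the data choose the weight, which under equal variances is the correlation. Randomisation makes both approaches unbiased for the V5 group difference, so the choice is about precision alone.

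With 24 people per arm precision is scarce, and the needed V1 values are already collected. At stake is a wider confidence interval than necessary for each Aim 3 outcome.

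**Working it through.** **Inputs.** N = 48, 24 per arm (Overview of Study Design). Repeated-measures correlation 0.4 (Sample size determination, for Aim 1). No correlation, effect size or power figure is given for Aim 3, so 0.4, 0.5 and 0.6 are assumptions here. I read the Aim 3 test as Group x Session, as in Aim 1.

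**The plan's own figure first.** The sample size was set "assuming 85% power at alpha=0.05 for detecting group by session interactions in Aim 1". The two-occasion Aim 1 case has the same shape as Aim 3. With f = d/2 = 0.2, the noncentrality is N f² m/(1−ρ) = 48 × 0.04 × 2/0.6 = 6.4 on 1 and 46 df, giving power 0.697 against the stated 70%. At d = 0.6 it is 0.960 against 96%. The stated figures reproduce.

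**Per-arm variance of the V5 contrast** (units of SD², equal variances and one common correlation ρ between all visits):

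- Change from V1: 2(1−ρ)
- Adjusted for V1: 1−ρ²
- Adjusted for V1 and screening: 1 − 2ρ²/(1+ρ)

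| ρ | Change | Adjusted for V1 | Adjusted for V1 and screening |
|---|---|---|---|
| 0.4 | 1.20 | 0.84 (30% less) | 0.77 (36% less) |
| 0.5 | 1.00 | 0.75 (25% less) | 0.67 (33% less) |
| 0.6 | 0.80 | 0.64 (20% less) | 0.55 (31% less) |

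The V1 step can never lose on these formulas: 2(1−ρ) − (1−ρ²) = (1−ρ)², which is not negative.

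**Where the gain comes from.** At ρ = 0.4 the total saving is 1.20 − 0.77 = 0.43, of which 1.20 − 0.84 = 0.36 (84%) comes from V1 alone. At 0.5 and 0.6 the V1 share is 75% and 64%. Screening removes a further 8%, 11% and 14% of the variance left after V1.

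**Standard error and power.** With SE = √(2 × variance/24) at ρ = 0.4, the SE is 0.316 SD for change, 0.265 adjusted for V1 and 0.254 adjusted for both. The noncentrality of 6.4 corresponds to a difference in change of √6.4 × 0.316 = 0.8 SD. For that difference, power by normal approximation is 0.72, 0.86 and 0.88. For 0.5 SD it is 0.35, 0.47 and 0.51. These are illustrations, because Aim 3 has no stated target effect.

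**If correlation decays with time.** Table 1 puts screening at Day −30 to −1, V1 at Day 7 and V5 at Day 35. Assume a first-order decay, with ρ the V1-to-V5 correlation. Once V1 is in the model, screening then adds nothing. The total reduction is the V1 reduction: 35% at ρ = 0.3, falling to 10% at ρ = 0.8. Under a common correlation the reduction over the same range is 38% to 28%.

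**What V3 adds.** With complete data and free means at each visit, including V3 leaves the V5-minus-V1 variance at 1.20 (ρ = 0.4). With 10% to 33% dropping out after V3 and ρ from 0.4 to 0.7, it lowers the variance by about 1% to 5%.

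**The case against.** The strongest defence is that nothing here is invalid. Aim 3 is labelled exploratory, its stated target is pre-to-post change, and V1 and V5 match both that target and the hypothesis in Purpose of the Study. The change comparison is unbiased under randomisation. The absence of covariates is inferred from a brief description, and the correlations are assumed. All of this stands, and it limits the point to precision and to a low priority. It does not remove the gain from V1 adjustment, which appears in every scenario checked.

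Four stronger readings are tempting, and the documents do not support them.

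- A reader might infer that the loss comes mainly from leaving screening and V3 out. Most of the saving at these correlations comes from how V1 is used, and Aim 3 already uses V1. V3 adds nothing to the V5 contrast when data are complete.
- A reader might infer that two pre-randomisation readings go unused. For quit self-efficacy and motivation to quit only the screening reading does. Pain-related cognitions also have A1, but that reading follows 24 hours of abstinence and is not a like-for-like baseline.
- A reader might infer that someone lost after V3 contributes nothing. The analysis section opens with mixed models and multiple imputation for hypothesis testing generally. With V1 on n people and V5 on m, a likelihood-based model has variance (1−ρ²)/m + (1−ρ)²/n, against 2(1−ρ)/m for completers only, so the V1 value still counts.
- A reader might call V1-to-V5 change the noisiest estimate available. At ρ = 0.6 a V5-only comparison has variance 1.00, against 0.80 for change.

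**Conclusion.** The point holds as one of efficiency. As described, Aim 3 is a change-score comparison, and adjusting V5 for V1 would cut the variance by 30%, 25% or 20% at correlations of 0.4, 0.5 or 0.6. Adding screening brings the total to 36%, 33% or 31% if the correlation is the same between all visits, and adds little if it decays. The formulas treat the regression slopes as known. Estimating them from 48 people gives back a little of the gain, which matters most for the small screening step.

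The consequence is modest: the aim is exploratory, and no conclusion of the plan depends on its power. It is least certain for pain catastrophizing and pain self-efficacy, since optional scales may not be given at every visit that Table 1 marks.

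**What to change.** Amend the Exploratory Aim 3 paragraph, before unblinded data are examined, to state that:

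1. the target is the group difference at V5;
2. the model adjusts for the V1 value of the same measure, and for its screening value where that was collected;
3. V3 and V5 are the outcome visits in a mixed model with Group x Visit, with baseline slopes allowed to differ by visit, and the V5 contrast is the one reported;
4. V3 is there mainly to support missing V5 values. If an average or trend over the treatment period is wanted instead, that is a different target and should be named.

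The plan should also say whether the catastrophizing and pain self-efficacy scales will be administered, and at which visits. If the sponsor prefers to keep V1-to-V5 change, one sentence giving the reason would do. The cost is analysis-plan wording only, with no new visit, questionnaire or participant.

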Baseline Abstinence/Training Session. Following screening, participants will complete a baseline abstinence challenge session, in which they are asked to abstain from smoking for 24 hours prior to the session. Expired CO < 6 ppm or 50% reduction from baseline will be used to verify abstinence. Participants will complete measures of craving, pain, and withdrawal. At the conclusion of the session, Metric Wire software will be installed on their smartphone, and they will be trained in the procedures for EMA.

Weekly Sessions. After one week of baseline EMA while smoking of usual brand cigarettes, participants attend an in-person visit (V1), during which they will be randomized to NNC or VLNC condition, given a supply of study cigarettes, and provided with a schedule of 4 weekly follow-up visits (V2 through V5). During each of the weekly visits participants will complete self-report measures and a timeline follow-back of past-week smoking, other tobacco use and alcohol/substance use; additional study cigarettes will be supplied; and breath CO and urinary measures of nicotine exposure will be collected. Adverse events will be monitored, as well as changes in medical history including new or discontinued medications, new treatments for current medical problems, or other study participation.

Post-Intervention Abstinence Session. Immediately following the final weekly visit, participants will be asked to abstain from smoking for 24 hours prior to attending a final laboratory abstinence session. Procedures and measures will be identical to those used in the initial abstinence session.

Follow-Up 3-Month Phone Call. Participants will be contacted by phone 3 months after completing the study to provide information about current smoking, recent quit attempts, and cessation strategies used.

Table 1. Schedule of Events and Procedures

CIGARETTES		UB	NNC	NNC or VLNC Cigarettes							
REMOTE ASSESSMENT		EMA			E			EMA			
IN-PERSON VISITS	Screening	24hr / Test 1 Traini (A1)	./ ng	Visit Week 1 (V1)	Visit Week 2 (V2)	Visit Week 3 (V3)	Visit Week 4 (V4)	Visi We 5 (V5	ek A	ABS Test 2 A2)	
Study Day	-30 to -1	0		7	14	21	28	35	3	36	
Window (in days)		0		(± 2)	(± 2)	(± 2)	(± 2)	) (±	2) (	± 1)	
PROCEDURES					-						
Informed Consent	Х								Î		
Eligibility	Х										
Demographics	Х										
Medical History	Х										
Tobacco History	Х										
Breath CO Sample	Х	Х		X	Х	Х	Х	Х	>	(	
Breath Alcohol	Х	Х		X	Х	Х	Х	Х	>	(	
Urine Drug Screen	х										

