### Exclusion criteria

- actively taking steps to quit smoking;
- inability to attend all required experimental sessions;
- report of significant health problems including but not restricted to untreated chronic hypertension, emphysema, seizure disorder, history of significant heart problems;
- systolic blood pressure > 160 or diastolic blood pressure > 100 (participants failing for blood pressure will be allowed to rescreen once);
- resting heart rate > 100 (participants failing for heart rate will be allowed to rescreen once);
- breath alcohol level > 0.000 (participants failing for BAL will be allowed to rescreen once);
- current use of prescription opioid pain relievers;
- lifetime history of bipolar or psychotic disorder;
- current unstable psychiatric disorder as assessed by the MINI;

- suicidal ideation with plan or intent; potential subjects who endorse items 4 (Active Suicidal
  Ideation with Some Intent to Act, without Specific Plan) and/or 5 (Active Suicidal Ideation with
  Specific Plan and Intent) on the Columbia Suicide Severity Rating Scale will be excluded from study
  participation, and referred to appropriate psychiatric treatment;
- use of non-cigarette tobacco products or electronic cigarettes > 8 times in past 30 days;
- current use of nicotine replacement therapy (NRT) or other smoking cessation strategy;
- use of Spectrum investigational cigarettes or low nicotine content cigarettes in the past year;
- quit attempt in the past 30 days resulting in greater than 3 days abstinence;
- past year alcohol or substance use disorder;
- use of illegal drugs as measured by urine drug screen (other than marijuana);
- daily or near-daily use of cannabis;
- primary pain complaint was due to specific medical conditions (e.g., cancer, rheumatoid arthritis, or complex regional pain syndrome);
- spine surgery within the past year or planned surgery within the timeframe of the study;
- positive pregnancy test among women

Changes to inclusion criteria made to reflect changes in criteria surrounding pain rating, now incorporating worst pain rating.

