### **Risk/Benefit Assessment**

• Include a thorough description of how risks and discomforts will be minimized (per 45 CFR 46.111(a) (1 and 2)). Consider physical, psychological, legal, economic and social risks as applicable. If vulnerable populations are to be included (such as children, pregnant individuals, imprisoned persons or cognitively impaired adults), what special precautions will be used to minimize risks to these subjects? Also identify what available alternatives the person has if he/she chooses not to participate in the study. Describe the possible benefits to the subject. What is the importance of the knowledge expected to result from the research?

Potential Risks: Continuing to smoke carries significant health risks. Participants enrolling in this study are not attempting to quit smoking, and will not be provided with smoking cessation treatment. However, participants will be provided with referral information for smoking cessation at the conclusion of the study. Use of VLNCs provided during the study does not pose any reduced risk relative to typical combustible cigarettes. There is a risk that participants in the VLNC condition could increase their smoking to compensate for lack of nicotine. Although infrequent, use of study cigarettes may also contribute to other adverse effects, including throat irritation, coughing, or nausea. There is also the risk that smokers assigned to the VLNC condition will experience increased withdrawal symptoms, including increased pain or negative affect due to decreased nicotine intake. All participants will be advised of potential symptoms and provided with coping strategies and support as necessary. Subjects may also experience withdrawal symptoms during 24-hr abstinence period. Finally, there is a risk attendant to the confidentiality of psychological data and self-report data.

There are no direct benefits to participants, but the study will increase knowledge of the role of nicotine and non-nicotine factors in the comorbidity between smoking and pain, and the effects of VLNCs on clinically-relevant outcomes among smokers with chronic pain. This information will aid in the development and evaluation of new and more effective treatments for smokers with pain. Given minimal risks of participation, we consider the risk/benefit ratio acceptable and representing an appropriate level of risk for human participation. Steps taken to minimize risks to participants are described below.

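### The analgesic sensitivity analysis codes no use at the two abstinence sessions and has no acetaminophen class, so as written it cannot serve the Hypothesis 1b pain model

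*Combined protocol and SAP*

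**What the plan says.** Under Data Analysis & Statistical Considerations, the Sensitivity Analyses paragraph sets out to examine the effect of "non-opioid analgesic use on the results of primary analyses". The rule for building the variable is "Analgesic use will be coded as yes/no at screening and at each weekly visit for the following medication classes", and the classes are "NSAIDS, anticonvulsants, antidepressants, other CNS depressants, muscle relaxants, migraine medications, and corticosteroids". The variable then enters the models: "Sensitivity analyses will then examine the impact of weekly use of each medication class as time-varying covariates in primary models".

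Specific Aim 1, in the same section, has two sets of models. One follows outcomes over the weekly visits V1 to V5. The other examines "pre-post intervention changes in withdrawal and pain following 24hr abstinence", with a two-level Session factor. Hypothesis 1b rests on this second set, and the first primary objective in the Research Summary names the abstinence challenge explicitly.

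The raw data are wider than the coding rule. The Medications row of Table 1 is marked at every in-person visit, and Design & Procedures adds that weekly visits record "changes in medical history including new or discontinued medications, new treatments for current medical problems, or other study participation". Opioids appear in the Exclusion criteria as "current use of prescription opioid pain relievers". Neither the coding rule nor the analysis text says how an opioid started during the study would be handled.

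**The concern.** Pain at A1 and A2 is the outcome of one of the two Aim 1 model sets, in people with chronic back pain who may take pain relief as needed. The Risk/Benefit Assessment accepts that pain could rise: "There is also the risk that smokers assigned to the VLNC condition will experience increased withdrawal symptoms, including increased pain or negative affect". If analgesic use differs between arms around A2, the A2 pain scores reflect medication as well as cigarette condition. The promised sensitivity analysis is where a reader would look to judge this, and on the stated rule it has no analgesic value at either occasion of that model.

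The class list raises a second problem, which affects the weekly models too. Acetaminophen is a non-opioid analgesic, so it falls within the stated scope, but it is not an NSAID and belongs to none of the other listed classes. A participant who takes nothing else is coded as a non-user in every class at every visit. The covariate then compares some users with a reference group that contains other users.

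**Working it through.** There is no plan figure to reproduce here. The check sets the visit schedule against the coding rule and the models.

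**Step 1: collected versus coded.** Table 1 has 8 in-person visits: screening, A1, V1 to V5 and A2. Its Medications row carries 8 marks, one per visit. The rule codes screening (1) plus the weekly visits (5), which is 6 of 8. The 8 − 6 = 2 uncoded visits are A1 and A2.

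| Visit | Study day | Medications collected | Analgesic use coded | Occasion in the abstinence model |
|---|---|---|---|---|
| Screening | −30 to −1 | yes | yes | no |
| A1 | 0 | yes | no | yes (pre) |
| V1 (randomisation) | 7 | yes | yes | no |
| V2 to V4 | 14, 21, 28 | yes | yes | no |
| V5 | 35 | yes | yes | no |
| A2 | 36 | yes | no | yes (post) |

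The abstinence model has 2 occasions, and 0 of 2 have a coded value. A time-varying covariate indexed by week has nothing to supply there.

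**Step 2: can a neighbouring visit stand in?** The plan already borrows V1 and V5 values of withdrawal and pain as pre and post covariates in a secondary abstinence analysis, so an analyst might do the same for analgesics. The text does not say so, and the timing is poor:
- For A1 (day 0), the nearest codes are screening, 1 to 30 days earlier, and V1, 7 days later.
- For A2 (day 36), the nearest is V5 (day 35). Design & Procedures starts the second abstinence period once V5 is over, so V5 coding cannot include anything taken during those 24 hours.

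**Step 3: class list.** Seven classes are named. None is acetaminophen, none is a residual analgesic class and none is opioids. An acetaminophen-only user is therefore coded no in 7 of 7 classes.

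**Step 4: which occasion can carry treatment-related bias?** A1 (day 0) precedes randomisation at V1 (day 7), so use at A1 can differ between arms only by chance. A2 follows randomisation, so use there can be affected by the assigned cigarette. For the same reason, entering A2 use as a covariate conditions on something the treatment may have changed. Adjustment alone would not remove bias.

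**The case against.** The strongest reply is that little is lost, because the data exist.

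- **Collection.** A reader might infer that the trial keeps no medication record at the abstinence sessions and that relief taken there could never be seen. Table 1 does not support that: medications are recorded at A1 and A2, and the second session repeats the procedures of the first. The gap is in the coding rule. Whether the form also asks about doses in the preceding 24 hours is unknown, since its items are not shown.
- **V5 is close to A2.** Stable, regular medication would normally show at V5. That is fair. What stays uncovered is as-needed or newly started medication over roughly one day, which is the day the test is about.
- **Opioids.** It is tempting to call their absence an error. The analysis is expressly limited to non-opioid drugs, current prescription users are excluded at entry, and new medications are recorded. The scope is deliberate. Only the handling of opioids started on study is open.
- **Direction.** A reader might infer that the gap favours VLNC cigarettes. The documents do not establish this. Both arms abstain before A2, and the plan predicts less pain in the VLNC arm there. If pain drives use, that would mean more medication in the NNC arm and a bias towards no difference.
- **Rescoring pain.** Counting any pain score obtained after an analgesic as a worse result would change the estimand and penalise stable users whose medication never changed. It is not needed for this point.

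The objection therefore limits how far the point reaches, but it does not answer the mismatch between the coding rule and the abstinence model, or the missing acetaminophen class.

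**Conclusion.** The point holds in limited form. The plan promises an analgesic check on its primary analyses, but the coding rule covers 6 of 8 visits and neither of the two occasions in the Hypothesis 1b pain model, so the check cannot be applied there as written. Separately, acetaminophen-only users are misclassified as non-users in every model that uses the variable.

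The consequence is confined to a sensitivity analysis, and the primary estimate is unaffected. Only A2 can carry treatment-related bias. Its size and direction cannot be derived, because the documents give neither analgesic use rates nor effects on pain. The conclusion rests on reading the rule and its class list literally, and on acetaminophen not being classed as an NSAID. It should be corrected because the promised check otherwise misses one of its target models and the repair is cheap.

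**What to change.** In the Sensitivity Analyses paragraph:

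1. Add A1 and A2 as coding points, using the medication record already taken there, and state that these values are the ones used in the abstinence model. Include use in the 24 hours before the session, adding one line to the form if it does not already ask.
2. Add an acetaminophen class, and a separate flag for opioids started after enrolment.
3. Tabulate use and new starts by arm at A1, V1 to V5 and A2, beside the pain results. Readers can then see any imbalance at A2 directly, without relying on adjustment for a post-randomisation variable.

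The cost is SAP wording, a few extra codes, one table and possibly one form line. Class coding at A1 and A2 can be done from existing records before analysis. Use in the preceding 24 hours is hard to recover afterwards, so if a form line is needed it should go in before further participants reach those sessions.
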